9.2.3 Study visits

The abstracted data will be recorded on the case report form (CRF). **Table 1** shows the collected data at different retrospective period of the medical chart.

Table 1 Data collection schedule

| Variables | Time points | Eligibility assessment | Data collection retrospectively | | |
|----------------------------------|-------------|------------------------|---------------------------------|-------------------------|--------------------------------------|
| | | | Before the index date | Index date [#] | 1-year follow-up period [†] |
| Eligibility assessments | X | | | | |
| Demographics ¹ | | | | X* | |
| Diagnosis of COPD ² | | | | X* | |
| Smoking status ³ | | | | X* | |
| Comorbidity ^{4, §} | | X [◊] | X | X | |
| COPD assessments [‡] | | | | | |
| CAT ⁵ | | X ^Δ | X | X | |
| mMRC ⁶ | | X ^Δ | X | X | |
| Examinations [‡] | | | | | |
| Spirometry data ⁷ | | X ^Δ | X | X | |
| Eosinophils | | X ^Δ | X | X | |
| Records [‡] | | | | | |
| Acute exacerbations ⁸ | | X ^{&} | X | X | |
| Hospital admissions ⁹ | | X ^{&} | X | X | |
| Treatments | | | | | |

| Variables | Time points | Eligibility assessment | Data collection retrospectively | | |
|--|-------------|------------------------|---------------------------------|-------------------------|--------------------------------------|
| | | | Before the index date | Index date [#] | 1-year follow-up period [†] |
| Related to COPD ^{10, \$} | | | X ^{11, ♦} | X | X |
| Related to comorbidities ^{12, \$} | | | X [◊] | X | X |
| Rescue treatments ^{13, ‡} | | | X [◊] | X | X |
| Oxygen therapy ^{14, \$} | | | X [◊] | X | X |
| Others ^{15, \$} | | | X [◊] | X | X |

[#]Not later than 30 June 2018; defined as the date of COPD patients in the cohort A and B starting using LABA/LAMA therapy regardless of new initiation or switching from other single/dual/triple treatment, or the date of the patients in the cohort C starting using LAMA treatment

[†]Not later than 1 year after the index date

^{*}The data nearest to the index date will be collected.

[◊]The data 6 months before the index date will be documented.

^{\$}The data will be collected every 6 months (allowed window: ± 1 month).

[‡]All available data on the medical chart will be recorded.

[△]The data nearest to the index date will be collected as the **Baseline**.

[&]The data/events ever since patients started receiving LABA/LAMA or LAMA therapy will be collected (maximum: trace back to 1 year before the index date).

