9.3.2.2 Secondary outcomes

- Annualized rate of mild/moderate/severe exacerbation
- Time/reason (e.g., severe airflow limitation, diagnosis of asthma, worsening exacerbation) from LABA/LAMA escalating to LABA/LAMA/ICS or from LAMA to dual therapy

Proprietary confidential information © 2019 Boehringer Ingelheim International GmbH or one or more of its affiliated companies

- Percentage of patients receiving LABA/LAMA switched to triple therapy or LAMA switched to dual therapy
- Change in pulmonary function after LABA/LAMA or LAMA initiation
- Use of rescue medications

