9.3.3.3 Acute exacerbation of COPD

The data from 1 year before the index date until death or 1 year after the index date should be collected.

Acute exacerbation is defined as a complex of lower respiratory events/symptoms (worsening or new onset) related to the underlying COPD, with a duration of 3 days or more, requiring a prescription of antibiotics and/or systemic steroids and/or hospitalization (should all be accompanied by code of ICD-9-491.21 or ICD-10-J44.1). Within the retrospective period, the onset/stop date of COPD exacerbation, severity* (mild, moderate, severe), and its outcome (leading to hospitalization/acute respiratory failure [ICD-9-518.81 or ICD-10-J96.00/J96.01/J96.02] or not) will be recorded. In terms of the exacerbation-related therapies, they will be recorded onto the page of “Rescue treatments” in the CRF.

***Mild exacerbation** is a patient with worsening but self-managed symptoms.

Moderate exacerbation is a patient receiving an exacerbation-related prescription such as oral corticosteroid (prednisone or prednisolone) and/or antibiotic, but not requiring hospitalization.

Severe exacerbation is a patient requiring hospitalization or emergency room visit due to COPD (ICD-9-491.21 or ICD-10-J44.1).

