9.3.3.4 COPD assessment test (CAT)

The data nearest to the index date will be collected as the **Baseline** and will continue recording until death or 1 year after the index date.

The COPD assessment test (CAT) is a simple, 8-item, health status instrument which provides a simple method for assessing the impact of COPD on the patient's health and the quality of life. The total CAT score ranging from 0 - 40 is calculated by summing the points for each variable. A decrease in CAT score represents an improvement in health status, whereas an increase in CAT score represents a worsening in health status.²¹ The most reliable estimate of the minimum significant difference in the CAT score is 2 points.²²

9.3.3.5 modified Medical Research Council dyspnea scale (mMRC)

The data nearest to the index date will be collected as the **Baseline** and will continue recording until death or 1 year after the index date.

mMRC is a 4-item questionnaire for measuring the severity of dyspnea of patients, and the score is correlated with health status²³ and mortality^{24,25} for patients with respiratory disease. If mMRC scale of the patient is > 2, it means the patient may suffer from dyspnea.

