9.7.1 Main analysis

The propensity score matching approach* will be used to balance the baseline characteristics between the study cohorts. These data will be compared descriptively between patients receiving different regimens (Tio + Olo vs. other LABA/LAMA vs. LAMA). If the propensity score matching is done, the difference before and after matching will be considered both.

For the primary outcome

Time to the first moderate or severe COPD exacerbation will be compared between different cohorts using Kaplan-Meier curves with the incidence and time to events, and statistical significance will be assessed using log-rank tests.

Time to first acute exacerbation starts from the index date to the date of the first acute exacerbation recorded on the CRF. Patients with exacerbation free at the time of escalating to ICS or no documented with exacerbations will be censored.

For secondary outcomes

- Time to escalating to dual/triple therapy will also be analysed using Kaplan-Meier curves and log-rank tests.
- The annualized rate of exacerbation with various severity will be calculated for each study group (episodes/patient-year), and the differences between the three cohorts will be compared by rate ratio.
- Results of lung function (i.e., spirometry data) and COPD assessments (i.e., CAT and mMRC) will be evaluated by the change from baseline. Pair *t*-test or other applicable statistical methods will be used for assessing the intra-group difference under a significance level of 0.05.
- Chi-square test or Fisher's exact test will be applied for categorical variables such as reasons for switching/escalating therapies, frequency, and percentage, etc.

*NOTE: Variables may include but not limited to age, gender, disease duration before index date, smoking status, body mass index, COPD assessment score (e.g., CAT and mMRC), spirometry data (e.g., FEV₁), oxygen therapy, comorbidities, disease severity, previous exacerbation, previous treatments, or eosinophil counts, where appropriate.

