9.9 LIMITATIONS OF THE RESEARCH METHODS

Data collection

A retrospective study is a suitable design to obtain instantly enormous information on the use of medications and their outcomes under the clinical practice. However, data integrity may be limited by data availability in the medical chart. The lack of data of interest may be one of the limitations. Considering the characteristics of COPD, the data regarding relevant assessments (CAT, mMRC, or spirometry) and medications for COPD are common tools to manage the disease progression. Sponsor, designated personnel, and sites will do their best to collect the available data of interest.

Unbalanced patients' characteristics

This study is a non-randomized retrospective study, which means the characteristics of enrolled patients may be imbalanced and influential to study endpoints. Hence, this study plans to apply propensity score matching for the study cohorts to balance the baseline characteristics. Significant difference between patients using different regimens is easier to be observed after the baseline matching.

Patient pool

The sample size of COPD patients using tiotropium/olodaterol (Spiolto[®]) may be less because this product is late on the market in Taiwan on April 18, 2016. To screen more possible patients, the entry criteria are non-restrictive and will permit data collection from a broad patient population.

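### Change in CAT, mMRC and spirometry is tested without any rule keeping out values taken during an exacerbation, so it may partly measure recovery from, or entry into, an exacerbation

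*Combined protocol and SAP*

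**What the plan says.** Section 9.7.1 states that lung function results and "COPD assessments (i.e., CAT and mMRC) will be evaluated by the change from baseline". A paired t-test or another suitable method "will be used for assessing the intra-group difference under a significance level of 0.05". Section 9.3.2.2 lists "Change in pulmonary function after LABA/LAMA or LAMA initiation" as a secondary outcome. CAT and mMRC are not listed there, but 9.7.1 analyses them under the secondary outcomes.

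Sections 9.3.3.4 (CAT), 9.3.3.5 (mMRC) and 9.3.3.6 (spirometry) use one baseline rule: "The data nearest to the index date will be collected as the" baseline, with recording then continuing until death or one year. For follow-up, the Table 1 footnote in 9.2.3 says "All available data on the medical chart will be recorded". No section says which follow-up value enters the change.

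The criteria in 9.2.2 do not exclude a patient who is in, or has just had, an exacerbation at the index date, and 9.9 says "the entry criteria are non-restrictive and will permit data collection from a broad patient population". Section 9.3.3.3 requires "the onset/stop date of COPD exacerbation, severity* (mild, moderate, severe), and its outcome" to be recorded from one year before to one year after the index date. The plan does not link these dates to the CAT, mMRC or spirometry values.

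**The concern.** CAT, mMRC and FEV1 can be expected to worsen during an exacerbation and recover afterwards. The index date is a treatment start or switch, and the plan expects some switches to accompany exacerbations: 9.3.3.2 records reasons for switching medication within exacerbation hospitalisations, and the abstract collects switch reasons from before the index date. A rule that looks only at nearness can therefore select an acute baseline. A follow-up value recorded at an exacerbation visit can enter in the same way.

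If acute values are more common at baseline, recovery is counted as improvement after starting the regimen. If they are more common at follow-up, a real improvement is hidden or a false worsening appears. The within-cohort test has no comparator to absorb either effect. What is at stake is the lung function secondary outcome and the CAT and mMRC change results, together with any descriptive comparison of these changes across the three cohorts.

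**Working it through.** The plan gives no expected change, SD or power for these measures, so there is no stated figure to reproduce. The check has two parts.

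**1. Reading the selection rules together**

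| Step | Rule | Condition on exacerbation |
|---|---|---|
| Eligibility (9.2.2) | COPD, age, regimen and excluded diagnoses | None |
| Baseline (9.3.3.4-9.3.3.6) | Nearest to the index date | None |
| Follow-up (Table 1) | All chart values up to one year | None |
| Analysis (9.7.1) | Change from baseline, within-cohort test at 0.05 | None |
| Limitations (9.9) | Missing data, imbalance, patient pool | Not mentioned |

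The stated rules therefore admit exacerbation-state values at both ends of the change.

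**2. Illustrating the size**

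Inputs from the documents: about 300 patients in the tiotropium/olodaterol cohort and rates of 0.78 and 0.90 exacerbations per patient-year (9.5), and a 2-point minimum difference for CAT (9.3.3.4).

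Assumptions, not in the documents: acute share of baseline values 10-30%; acute shift 4-6 CAT points; SD of change 6-8 points; two-sided test (9.7.1 does not say); 300 complete pairs.

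*Share of follow-up values that are acute.* If values fall at random in time, share = rate x window / 365. An assumed window of 14 to 42 days gives 0.78 x 14/365 = 3% to 0.90 x 42/365 = 10%. Visits prompted by symptoms could push the share higher.

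*Net bias* = (acute share at follow-up - acute share at baseline) x acute shift. Negative means a spurious CAT improvement.

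*False-positive rate with no true change* = P(|Z + bias/(SD/√n)| > 1.96).

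| Baseline share | Follow-up share | Shift | Bias (CAT points) | Rate, n = 300, SD 8 | Rate, n = 300, SD 6 |
|---|---|---|---|---|---|
| 10% | 10% | 4-6 | 0 | 5% | 5% |
| 10% | 3% | 4 | -0.28 | 9% | 13% |
| 20% | 7% | 5 | -0.65 | 29% | 47% |
| 30% | 10% | 6 | -1.20 | 74% | 93% |
| 30% | 3% | 6 | -1.62 | 94% | over 99% |
| 5% | 10% | 5 | +0.25 | 8% | 11% |

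For example, the third row: (0.07 - 0.20) x 5 = -0.65; with SD 8 the standard error is 8/√300 = 0.46, so the shift is 1.41 standard errors and the rate is 29%. The last row lies outside the assumed baseline range and is there to show the reversal.

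*FEV1*, assuming 150 pairs, SD of change 250 mL and an acute fall of 100-200 mL (standard error 250/√150 = 20.4 mL). Equal shares give 0 mL and 5%. Shares of 10% and 3% with a 100 mL fall give a false gain of (0.10 - 0.03) x 100 = 7 mL and 6%. Shares of 30% and 3% with a 200 mL fall give 54 mL and 75%.

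**The case against.** The best reply is that nothing in the documents shows index prescriptions clustering at exacerbations. This is fair. The example of worsening exacerbation in 9.3.2.2 is a reason for escalating away from the index regimen, so it concerns follow-up. Table 1 marks nearly every variable at the index date, so its mark for exacerbations proves nothing. The link rests on the switch reasons mentioned above, which show that the situation is foreseen but not how often it occurs.

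Three stronger readings are tempting, and the documents do not support them.

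- *The tests will report false improvement.* A reader might multiply the baseline share by the shift, but that sets the follow-up share to zero. The difference in shares governs, and it can be zero or reversed.
- *The cohorts are biased differently because A and B accept switchers and C only new starts.* This is possible, but no figure in the plan bears on it.
- *Propensity matching and eosinophils need the same restriction.* Eosinophils are not in the change analysis. Acute state at prescribing may itself influence regimen choice and prognosis, so removing it from the matching variables could discard confounder information.

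It is also true that 300 pairs is optimistic, because values are recorded only when the chart has them, and that an uncontrolled within-group change cannot be attributed to the regimen even with stable values. Finally, the contents list redacts an entry between 9.7.1 and 9.7.3, and the data validation plan is not provided. A rule there cannot be excluded, but the baseline definitions and 9.7.1 refer to none.

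**Conclusion.** The concern holds as a gap in the definition of the analysis values. As written, 9.3.3.4-9.3.3.6 and 9.7.1 allow exacerbation-state values into the change in CAT, mMRC and spirometry at either end. Under the assumed ranges the spurious CAT improvement is 0 to about 1.6 points against the 2-point minimum difference, and the false-positive rate at 300 pairs is about 5% to nearly 100%. The width of that range is the finding: the plan has no rule that keeps the effect near the low end. The high end needs a large imbalance in acute shares and a large acute shift, and fewer pairs would lower it. The definition of the primary outcome, time to first moderate or severe exacerbation, is not affected. The gap is worth closing because the remedy relies mainly on dates the study already collects.

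**What to change.** In 9.7.1, for the change analyses of spirometry, CAT and mMRC only, define the baseline and follow-up values as the nearest ones not taken between the recorded onset and stop of an exacerbation, or within a recovery interval after it. Fix the length of that interval before the change data are examined. Report the unrestricted analysis alongside. Where no stable value was abstracted, flag the acute-window value and exclude it from the restricted analysis. Report the number excluded in each cohort.

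Leave the propensity-score covariates and the eosinophil rule as planned, with at most a sensitivity analysis.

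Cost: a paragraph of text and a date comparison. Onset and stop dates are already collected. The plan states an assessment date explicitly only for eosinophils (9.3.3.2), so confirm that the CRF dates each CAT, mMRC and spirometry value; a nearest-value rule needs those dates anyway. This version is dated 25 November 2019 and data collection is planned to end on 30 November 2019, so further abstraction of stable values may not be practical. Flag-and-exclude still works in that case.

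Downside: pairs are lost, and imputation is not allowed (9.7.3). If 30% were lost without replacement, intervals would widen by 1/√0.70 - 1, about 20%. Patients without a stable value may also differ from the rest, which is why the exclusions and the unrestricted result should be shown together.

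### In the visible plan, change in spirometry, CAT and mMRC gets only a within-cohort significance test, which cannot attribute change to treatment; a baseline-adjusted between-cohort estimate should be added

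*Combined protocol and SAP*

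**What the plan says.** Section 9.3.2.2 lists "Change in pulmonary function after LABA/LAMA or LAMA initiation" as a secondary outcome. Change in CAT and mMRC is not on that list, but Section 9.7.1 analyses it alongside spirometry.

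In Section 9.7.1 the three measures "will be evaluated by the change from baseline". The method is a paired t-test "or other applicable statistical methods", and it "will be used for assessing the intra-group difference under a significance level of 0.05". The open alternative therefore keeps the same within-cohort target.

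Other outcomes in Section 9.7.1 are treated differently. Time to first exacerbation and time to escalation are compared by log-rank test, and for exacerbation rates "the differences between the three cohorts will be compared by rate ratio".

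One sentence could bring the comparators in: "These data will be compared descriptively between patients receiving different regimens". In Section 9.7.1 it follows the sentence on balancing baseline characteristics. In the Abstract (Section 4, data analysis) the same sentence can be read as covering all abstracted data.

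On measurement, Section 9.3.3.4 says "The data nearest to the index date will be collected as the" baseline, with no time window. Sections 9.3.3.5 and 9.3.3.6 do the same for mMRC and spirometry. For follow-up, a footnote to Table 1 in Section 9.2.3 says "All available data on the medical chart will be recorded". No time point is fixed for the change, and Section 9.7.3 rules out imputation.

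**The concern.** A paired test asks whether mean change differs from zero. It has no control, so three other explanations stay open:

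- **Regression to the mean.** Baseline is a single value close to the start or switch of therapy, when patients may be worse than their usual state.
- **Time trend.** Values may drift over the year whatever the drug.
- **Selective remeasurement.** Only patients with a later chart value contribute, and nothing ensures that they represent the cohort.

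The cohorts also differ in size, and so in the power of the within-cohort test. Three p-values side by side invite the reader to take significance in one cohort but not another as a difference between regimens. At stake is the interpretation of one listed secondary outcome and two supporting measures. The primary outcome is not touched.

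**Working it through.** The documents give no SD, effect size, power or sidedness for these changes, so there is no planned figure to reproduce. Two-sided 0.05 is taken throughout.

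**Inputs from the documents.** Cohort A about 300 and cohort B about 800 (Section 9.5). Cohort C about 1,800 − 300 − 800 = 700, by subtraction. A difference of 2 CAT points as the minimum significant difference (Section 9.3.3.4).

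**Assumed inputs, with ranges.** Within-patient correlation ρ from 0.6 to 0.9. Baseline worse than usual by d = 0.1 to 0.5 baseline SD. SD of CAT change 5 to 11 points. SD of FEV1 change 0.20 to 0.30 L.

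**1. No drug effect, regression to the mean only.** Mean shift = (1 − ρ)d; SD of change = √(2(1 − ρ)), both in baseline-SD units. With k = shift/SD × √n, P(significant) = Φ(k − 1.96) + Φ(−k − 1.96).

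For ρ = 0.8 and d = 0.25, the shift is 0.2 × 0.25 = 0.05, the SD is √0.4 = 0.632 and their ratio is 0.079.

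| n | k | P(significant) |
|---|---|---|
| 300 | 1.37 | 27.8% |
| 700 | 2.09 | 55.2% |
| 800 | 2.24 | 60.9% |

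Over the assumed ranges the probability runs from 6.7% to 97.2% at n = 300 and from 9.7% to 100% at n = 800, against a nominal 5%.

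**2. Same true change in A and B.** Within-cohort power is Φ(δ√n − 1.96) + Φ(−δ√n − 1.96). For a standardised change δ = 0.10 it is 41.0% at n = 300 and 80.7% at n = 800. The chance that exactly one is significant is 0.410 × (1 − 0.807) + 0.807 × (1 − 0.410) = 55.5%. It is 35.1% at δ = 0.05 and 26.7% at δ = 0.15.

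**3. Number of tests.** Three measures in three cohorts make nine tests: 1 − 0.95^9 = 37.0% familywise error if independent. No multiplicity control is stated for them.

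**4. Detection threshold for FEV1.** 1.96 × SD/√300 gives 22.6 mL at SD 0.20 L and 33.9 mL at SD 0.30 L. If only 150 patients have paired values (assumed), it is 32 to 48 mL. This measures the sensitivity of the test, not the size of any regression to the mean.

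**5. Is a between-cohort estimate feasible?** For a 2-point CAT difference, A 300 against B 800: SE = SD × √(1/300 + 1/800) = 0.0677 × SD; power = Φ(2/SE − 1.96); CI half-width = 1.96 × SE.

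| SD of change | Power, all paired | Half-width | Power, half paired | Half-width |
|---|---|---|---|---|
| 5 | >99.9% | 0.66 | 98.7% | 0.94 |
| 7 | 98.8% | 0.93 | 84.7% | 1.31 |
| 9 | 90.7% | 1.19 | 64.1% | 1.69 |
| 11 | 76.6% | 1.46 | 47.6% | 2.06 |

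A against C (about 700) is nearly the same: 98.5% at SD 7 with all pairs. Baseline adjustment would normally lower the SD further.

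**The case against.** The strongest defence is that the paired analysis answers the outcome as worded, since the listed outcome is itself a before-after quantity. The secondary objectives in Section 8 are descriptive, and the comparative interest set out in Sections 4 and 7 concerns exacerbations, which do get between-cohort methods. This stands, and it limits the weight of the point. It does not rescue the 0.05 threshold, because a significance test goes beyond description and invites an attribution that the design cannot support.

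A reader might infer that the plan ignores its comparators, or that the study cannot say whether change differs between regimens. The documents do not support either. The descriptive comparison in the Abstract may cover these changes, and the table of contents shows a redacted entry between 9.7.1 and 9.7.3 whose content is unknown. Nor can the comparators be called already matched, since Section 9.7.1 speaks of the results before and after matching only on condition that matching is done.

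A reader might also infer that regression to the mean has been shown. It has not. Section 9.2.2 sets no lung-function or symptom threshold for entry, and the wide range in step 1 shows how far the result depends on the assumptions. What holds whatever its size is that the test cannot exclude it. Likewise, the plan nowhere proposes to compare p-values across cohorts; that is a foreseeable misreading.

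Finally, adjustment is not a cure. Section 9.1 admits switchers to cohorts A and B but only new initiators to C, so regression to the mean may differ by cohort.

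**Conclusion.** The point holds for the visible text of Section 9.7.1: the only inference named for these changes is within cohort, and any between-regimen comparison is at most descriptive. A significant within-cohort change cannot be attributed to treatment, and differing significance across unequal cohorts is not evidence of a regimen difference. The first statement rests on the design alone. The size of the problem rests on assumed correlations, baseline shifts and SDs, and on available pairs, whose number the documents do not give. At the planned cohort sizes a between-cohort estimate is feasible, less so if many patients lack paired values and the SD is large. This is a worthwhile improvement to a secondary analysis. It is not an internal contradiction and does not affect the primary outcome.

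**What to change.** 1. Report within-cohort change as mean change with a 95% CI for FEV1 and CAT, and as a distribution of scores for mMRC, with no significance claim.
2. Add a between-cohort estimate with a 95% CI, adjusted for the baseline value. For FEV1 and CAT, use ANCOVA at a defined follow-up window, or a repeated-measures model with time since index that uses all recorded values. For mMRC, a 0–4 score, use an ordinal model.
3. Run it in the matched set if matching is done, otherwise with the propensity-score variables as covariates.
4. Include prior therapy (new initiation or switch) as a covariate where the cohorts overlap. Switchers in A and B have no counterpart in C, so state this limit for contrasts with C.
5. State how many patients in each cohort contribute paired values, and state that confounding and selective remeasurement may remain.

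The cost is one standard model per measure on data already to be collected, plus a rule for the follow-up window if ANCOVA is chosen. The estimates will still depend on available pairs. If the redacted section already contains such an analysis, a cross-reference from Section 9.7.1 would cover item 2.

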9.2.1 Study sites

Selected sites include around 12 medical hospitals with the highest level in Taiwan from Northern to Southern area. Further, these hospitals have adequate patient pool and sufficient clinical data for collection.

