9.4 DATA SOURCES

No additional diagnostic or monitoring procedures will be applied to the patients because of a retrospective study, and this study plans to collect the data onto the designed CRF as only those are available in the medical records. The data source includes medical records in ~ 12 hospitals in Taiwan, where pulmonologists licensed with specialty care for respiratory diseases (COPD included) and critical care medicine.

Each patient is identified by a unique subject/initial number, which is only used for study purposes.

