9.5 STUDY SIZE

Based on the projected market share and per physician's clinical experience, data from approximately 1,800 patients will be collected.

Among these patients, using Tio + Olo FDC versus other LABA/LAMA therapy (FDC or free combo) is assumed the ratio of 1:2 (~ 300 Tio + Olo, ~ 800 other LABA/LAMA therapy). If we assume the same annualized event rates as in the Taiwanese subgroup analysis report of DYNAGITO¹ (i.e. 0.78 per patient-year for Tio + Olo and 0.90 per patient-year for other

therapies), expecting the 95% CI for incidence rate ratio to be 0.87 (0.768, 0.978), with good precision. The following **Table 2** also shows that with smaller sample size, the precision is reduced (wider 95% CI).

Table 2 Sample size estimation

| Tio + Olo | | Other | | Incidence rate ratio (95% CI) |
|---------------------|-------------|---------------------|-------------|-------------------------------|
| True Incidence rate | Sample size | True Incidence rate | Sample size | |
| 0.78 | 300 | 0.90 | 800 | 0.87 (0.768, 0.978) |
| 0.78 | 300 | 0.90 | 300 | 0.87 (0.751, 1.000) |
| 0.90 | 300 | 0.97 | 800 | 0.93 (0.829, 1.039) |
| 0.90 | 300 | 0.97 | 300 | 0.93 (0.810, 1.062) |
| 0.90 | 200 | 0.97 | 200 | 0.93 (0.786, 1.094) |
| 0.90 | 200 | 0.97 | 100 | 0.93 (0.734, 1.173) |

In this table, it is assumed that all patients have on average ~ 2 patient-year exposure.

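### Section 9.7.1 does not commit to adjusting for hospital, so the cohort comparison may be confounded if both prescribing and event recording differ between the roughly 12 hospitals

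*Combined protocol and SAP*

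**What the plan says.** Section 9.7.1 plans propensity score matching to balance the three cohorts: Tio + Olo, other LABA/LAMA, and LAMA. The note on variables begins "Variables may include but not limited to age, gender, disease duration before index date, smoking status, body mass index, COPD assessment score" and ends "oxygen therapy, comorbidities, disease severity, previous exacerbation, previous treatments, or eosinophil counts, where appropriate". Everything named is a characteristic of the patient. The list in the Abstract (Section 4) is the same.

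For the primary outcome, time to first moderate or severe exacerbation, the cohorts are compared by Kaplan-Meier curves and "statistical significance will be assessed using log-rank tests". For the annualized rates, "the differences between the three cohorts will be compared by rate ratio". Neither statement mentions strata, covariates or a site effect.

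On the setting, Section 9.2.1 says "Selected sites include around 12 medical hospitals with the highest level in Taiwan from Northern to Southern area". Section 9.3.3.3 requires that the prescriptions or admissions defining an exacerbation "should all be accompanied by code of ICD-9-491.21 or ICD-10-J44.1". Section 9.4 adds that "this study plans to collect the data onto the designed CRF as only those are available in the medical records". Section 9.9 lists imbalance in patients' characteristics as a limitation but says nothing about differences between hospitals.

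**The concern.** Whether an event enters the data depends on what a hospital's staff wrote and coded in the chart. Severe events are admissions or emergency visits, so local admission practice may also shape the endpoint. Which LABA/LAMA product a patient received may likewise vary by hospital. Section 9.9 notes that Tio + Olo reached the Taiwanese market only in April 2016, so uneven uptake by June 2018 is plausible.

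If both vary together, hospital is a confounder. Balancing the named patient variables need not remove it, because none of them identifies the hospital. At stake is the Tio + Olo comparison with each of the other two cohorts, where the effect assumed in Section 9.5 is small enough to be matched by a moderate hospital imbalance.

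**Working it through.** **The plan's own effect.** Section 9.5 assumes 0.78 and 0.90 events per patient-year, so the planned rate ratio is 0.78/0.90 = 0.867, shown there as 0.87. The stated interval (0.768, 0.978) follows from a Poisson log-rate-ratio standard error, √(1/(0.78·300·T) + 1/(0.90·800·T)), with T = 1.5 years. With the stated average of about 2 years it would be (0.781, 0.962). That mismatch is a separate matter. Only the ratio 0.867 is used below.

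**Crude illustration.** The documents give no figures by hospital, so these inputs are assumptions. There is no drug effect. One group of hospitals records 0.7 events per patient-year and the other 1.0. Let a and b be the fractions of the Tio + Olo and other-LABA/LAMA cohorts treated in the low-recording group. No matching is applied.

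False ratio = [0.7a + 1.0(1 − a)] / [0.7b + 1.0(1 − b)]

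| a / b | Tio + Olo | Other | Ratio |
|---|---|---|---|
| equal (any value) | same | same | 1.00 |
| 60% / 40% | 0.82 | 0.88 | 0.93 |
| 70% / 30% | 0.79 | 0.91 | 0.87 |
| 40% / 60% | 0.88 | 0.82 | 1.07 |
| 30% / 70% | 0.91 | 0.79 | 1.15 |

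The ratio is also 1.00 if recording is the same everywhere. On the log scale, 60/40 gives ln(0.932)/ln(0.867) = 0.49 of the planned effect, and 70/30 gives ln(0.868)/ln(0.867) = 0.99.

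With 300 and 800 patients, a 60/40 split means a Tio + Olo share of 180/(180 + 320) = 36% in low-recording hospitals and 120/(120 + 480) = 20% elsewhere. A 70/30 split means 210/(210 + 240) = 47% and 90/(90 + 560) = 14%.

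**How much would matching on previous exacerbations absorb?** Suppose both cohorts are matched exactly on the prior-year count, recorded under the same hospital habits. If patients within a hospital share one Poisson rate, almost nothing is absorbed: 0.932 becomes 0.933, and 0.868 becomes 0.870. If patients also vary by a gamma frailty of mean 1 and assumed shape 1 to 0.5, 0.932 becomes 0.963 to 0.975, and 0.868 becomes 0.928 to 0.950. The bias shrinks but does not vanish.

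**Type I error of the log-rank test.** The simulation used 1,100 unmatched patients, 12 hospitals, no drug effect, a mean allocation near 300:800, a baseline rate of 0.9 per year and one year of follow-up. Hospital effects on rate and on drug share were drawn independently. There were 1,500 runs per scenario, so the Monte Carlo error near 5% is √(0.05·0.95/1500) = 0.6 percentage points. Two-sided 5% is assumed.

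| Variation between hospitals | Unstratified | Hospital-stratified |
|---|---|---|
| None, or only one of rate and share | 4.6–5.5% | 4.5–5.7% |
| Log-rate SD 0.2, logit-share SD 0.5 / 1.0 | 6.6% / 8.7% | 5.8% / 4.8% |
| Log-rate SD 0.4, logit-share SD 0.5 / 1.0 | 8.0% / 17.7% | 4.6% / 4.7% |

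Error rises only when rate and share both vary. The stratified test stays near 5% throughout.

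**The case against.** The strongest reply is that the documents do not show the problem exists. All sites are of the same tier, one definition with the same codes applies everywhere, and Section 9.8 provides for training physicians on the protocol. This stands in part: no section says that prescribing or coding differs by hospital. It does not remove the risk. The index dates fall no later than 30 June 2018, so the follow-up charts were written before training in 2019 could affect them, and a common definition does not make past coding uniform.

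A reader might infer that the plan excludes hospital from the matching and so necessarily pairs patients across hospitals. The documents do not support that. The list of variables is expressly non-exhaustive, so hospital is unspecified rather than ruled out. What remains is the lack of a commitment, which leaves the choice open until the data have been seen. The log-rank and rate-ratio statements carry no similar open wording.

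The table of contents has one redacted line between Sections 9.7.1 and 9.7.3, and its text is not visible. It could contain analyses by site, so the point is limited to the main analysis.

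A reader might also infer that bias would persist at full size after ideal matching on the named variables. The calculation on previous exacerbations shows that matching may remove part of it.

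Nor is there support for treating within-hospital correlation as a separate harm. Error stayed at about 5% when only the rate or only the drug share varied.

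**Conclusion.** The point holds conditionally. Section 9.7.1 does not commit to adjusting for hospital in the propensity score, the log-rank test or the rate ratio. If the Tio + Olo share and event recording both differ across the hospitals, the comparison may be confounded in either direction. In the crude illustration the false ratio runs from 0.87 through 1.00 to 1.15, depending on the size and direction of the alignment, and matching on exacerbation history would probably bring it closer to 1. In the simulations, unstratified type I error was 6.6% to 17.7% when both factors varied, against 4.6% to 5.8% with stratification in the same scenarios. All these sizes rest on assumed differences between hospitals and on unmatched data. They show what could happen, not what this study's bias is. The change is a worthwhile and cheap improvement, not the correction of a demonstrated error.

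**What to change.** State in Section 9.7.1 that:

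- hospital enters the propensity model as a fixed term;
- the log-rank test (or a Cox model) is stratified by hospital;
- the rate ratio is stratified by hospital, by Mantel-Haenszel or with a hospital term in a rate model;
- cohort counts and crude event rates are tabulated by hospital, so that readers can see whether prescribing and recording vary together.

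Keep exact matching within hospital as a sensitivity analysis where numbers allow. About 300/12 = 25 Tio + Olo patients per hospital on average is thin for exact matching on top of the other named variables, across three cohorts and without imputation.

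The cost is a few sentences of text and a stratum statement in the programs. Hospital should be known for every patient, since source documents are filed at the site (Section 9.10.2.1). The downside is some loss of precision where a hospital contributes few patients to one cohort.
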